Written informed consent will be obtained from all potential subjects prior to their participation in this research. The informed consent process will be based upon principles discussed in the Declaration of Helsinki and in accordance with US 21CFR. Applicable HIPAA privacy notifications will be included. Participants will be given ample time and opportunities to ask questions about this study prior and following consent. All consent forms will require IRB approval prior to their use.

Patients will always have the right and will be informed of their right to withdraw from the study at any time. Enrolling clinicians will be made aware that the needs of their patients come first and thus the safety and wellbeing of study participants is of primary concern.

A Data and Safety Monitoring Board (DSMB) will review safety data on a quarterly basis through the first year of enrollment and then twice per year. A detailed data and safety monitoring plan will be submitted and approved by the Mayo IRB and by the funding entity (PCORI) prior to accrual of human subjects. Based upon the results of this review, the DSMB will make recommendations regarding study methods and continuation of the research.

The benefits of this proposed research study far outweigh the risks. As discussed in detail in the main body of this grant application, chronic migraine with medication overuse is a very common problem and one that exerts substantial negative impacts on the lives of people suffering with this condition. Despite its high prevalence, the significant burden that it causes, and the undeniable need for treating patients who have chronic migraine with medication overuse, the best treatment strategy is currently unknown. For the benefit of patients who have chronic migraine with medication overuse and their family members, it is essential that we move past this clinical equipoise and clarify the best treatment strategy. Given the design of this proposed study, the risks associated with participation are similar to those that a patient is exposed to during routine clinical care. Both treatment strategies used in this proposed research are commonly used in routine clinical practice. Each patient participant's enrolling clinician is also his or her treating clinician. Within the confines of the treatment strategy that an individual participant is randomized to, the clinician will utilize their best clinical skills for making treatment decisions, as would be done in

typical clinical practice. Adverse events will be managed just as they would be in typical clinical practice.

In all research involving human subjects, the loss of confidentiality is a principal concern. Therefore, steps will be taken to minimize this risk. All information collected from study participants will be locked in a secure location. Identifying information will be removed from the data forms and replaced by unidentifiable codes. Electronic databases/spreadsheets will be password protected and only accessible to those with access rights. (DN-1) Only de-identified data will be made widely available to other researchers. Data will be entered into Medidata Rave. Medidata Rave is the information technology system endorsed by Mayo Clinic's Clinical Trial Management System. The Medidata Rave system is compliant with 21 Code of Federal Regulations (CFR) Part 11 Food and Drug Administration (FDA) requirements. Edit checks, electronic queries, and audit trails are built into the system to ensure accurate and complete data collection and security. The Medidata Rave database access model is role based and fully auditable at the study, form, and field levels. Access is managed by the Mayo Clinic's Clinical Trial Management System Service and Solution Center, under a controlled and monitored access request system. Data will be transmitted via the Internet from investigational sites to the Mayo Clinic via state-of-the-art encryption mechanisms, thus ensuring security and confidentiality.

Women and minorities will be included in this study in proportions that represent the populations from which they are enrolled. Based upon the propensity of chronic migraine with medication overuse to impact women disproportionately more than men, we expect that 3.5 to 4 women will be enrolled into this study for every one man enrolled into this study. We anticipate that minorities will be enrolled in proportions that reflect the U.S. population, with approximately 35.6% of participants being of a race/ethnicity other than non-Hispanic white or European American. According to the 2010 U.S. Census of the total population (Hispanic and Non-Hispanic), 78.4% of the population is White, 13% of the population is Black or African American, 1.2% is American Indian or Alaska Native, 4.9% is Asian, 0.2% is Native Hawaiian and Other Pacific Islander, and 2.3% is two or more races. Hispanics accounted for 16.3% of the total U.S. population according to the 2010 Census. Thus, we anticipate that of the 720 enrolled patient participants, 576 will be women, 117 will be Hispanic, 564 will be White, 94 will be Black or African American, 9 will be American Indian or Alaska Native, 35 will be Asian, 1 will be Native Hawaiian or Other Pacific Islander, and 17 will be two or more races.

Children and adolescents under the age of 21 will not be included in this study. Although we considered including children and adolescents, their exclusion from this proposed study is based upon the facts that: 1) although little is known about the prevalence of medication overuse in the pediatric chronic migraine population, medication overuse is thought to be much less frequent among children and adolescents compared to adults; 2) the medications overused amongst children with medication overuse differ compared to the medications overused in adults; 3) the treatment strategies for treating children and adolescents who have chronic migraine with medication overuse differ from the strategies used when treating adults (e.g. onabotulinumtoxinA is approved for adult patients with chronic migraine but not for children or adolescents). Although additional investigations into chronic migraine with medication overuse in children and adolescents are needed, such investigations will be better performed in studies separate from this proposed PCORI study.

This study will not enroll participants from "vulnerable populations" (i.e. prisoners, pregnant women, children).

All investigators who participate in this trial will have to complete or demonstrate prior completion of education on the protection of human research participants. (DN-1) The principal investigators will require documentation that such training has been completed prior to investigators enrolling subjects into this study.

13. Informed Consent

Informed consent procedures will be performed according to the requirements and recommendations of each participating centers Institutional Review Board.

Written consent will be obtained from all subjects. Written consent can be obtained from the patient in the office, by using internet-based document software (e.g. DocuSign), by scanning paper documents and submitting them by e-mail, and by sending signed documents through regular mail. Only those methods that are IRB-approved will be used. Copies of consent forms will be submitted to the Mayo Clinic.

a. Informed Consent Personnel

Any member of the research team who obtains informed consent from a subject will need to be approved by their local IRB to do so.

b. Location and Privacy

The informed consent process will occur in a location that is approved by the local IRB.

c. Storage of Consent Documents

Consent documents will be stored at each participating center for a minimum of 3 years after conclusion of the study. The subject will be provided with a copy of the consent document. Copies of the consent documents will also be sent to the Mayo Clinic.

d. Withdrawal of Consent

Subjects will have the right to withdraw their consent at any time. After a participant withdraws from the study, they will not be contacted and their data will not be used moving forward.

14. Subject Retention

Telephone calls, e-mails, and other telehealth methods of communication with patients will help retain subjects and improve adherence rates. Only those methods that are IRB-approved will be used. The contact schedule can be seen above in section 9j.

Subjects will receive compensation of \$30 per research visit, including the baseline visit and 12-week follow-up visit. Including these two mandatory research visits, subjects can receive compensation for up to 6 research visits maximum during their 48 weeks of participation with this study.

After two days of not entering diary data, subjects will receive e-mails and/or text messages reminding them to record their data in the internet-based or mobile app headache diary. Subjects will receive \$50 compensation per 4-week period during which they are at least 80% compliant with providing headache diary data (i.e. provide diary data on at least 80% of days). Since subjects are asked to maintain the diary for five 4-week periods during the study (weeks 1-4, 5-8, 9-12, 21-24, and 45-48), the maximum compensation for diary compliance is \$250 per subject.

15. Data Management

Data will be entered into a Medidata Rave electronic database capture system. Medidata Rave is the information technology system endorsed by Mayo Clinic's Clinical Trial Management System. Study sites will enter data into electronic case report forms using Medidata Rave. Case report forms are automatically presented to site investigators based on a predetermined, visit based schedule in order to improve study staff workflow and data quality. The Medidata Rave system is compliant with 21 Code of Federal Regulations (CFR) Part 11 Food and Drug Administration (FDA) requirements. Edit checks, electronic queries, and audit trails are built into the system to ensure accurate and complete data collection and security. During the course of the data entry into Medidata Rave, the system provides real-time within case report form and inter-case report form data consistency verification. Medidata Rave is flexible in nature so that all data can be entered even if "required" fields and other consistency checks requirements are not satisfied. The system uses an internal "flagging" or "query" system to distinguish the valid from the invalid data thereby ensuring compliance with the Food and Drug Administration guidance document "Computerized Systems Used in Clinical Trials". The Medidata Rave database access model is role-based and fully auditable at the study, form, and field levels. Access is managed by the Mayo Clinic's Clinical Trial Management System Service and Solution Center, under a controlled and monitored access request system. Data will be transmitted via the Internet from investigational sites to the Mayo Clinic via state-of-the-art encryption mechanisms, thus ensuring security and confidentiality.

16. Adverse Events Reporting

The adverse event process flow from the National Institutes of Health National Institute on Aging will be used for this study. (see appendix) Investigators will immediately report all serious adverse events to their local Institutional Review Board and to the Principal Investigators. The Principal Investigators will immediately report all serious adverse events to the Data and Safety Monitoring Board and to the Mayo Clinic Institutional Review Board. All serious and non-serious adverse events will be recorded and submitted to the Data and Safety Monitoring Board. Adverse events will be recorded using the Adverse Event forms created by the National Institutes of Health National Institute on Aging (see appendix).

17. Protocol Maintenance

All protocol changes will be tracked within a Protocol Change Log and the revised protocol will receive a new version number and date. A description of the revision and the most recent protocol will be sent to each of the investigative sites. Investigators will be required to confirm receipt and review of the revised protocol.

18. Study Website

The study website is available at: www.motstrial.org

The website hosts the study protocol, updates on study progress, participating centers and links to presentations and publications that relate to this study.

19. Study Registration

The study has been registered with clinicaltrials.gov (NCT02764320; 5/4/16) and results will be reported to clinicaltrials.gov.

20. References/Citations

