B. Regular intake of simple analgesics (e.g. acetaminophen, NSAIDs) on \geq 15 days per month for >3 months

9. Study Procedures

Consecutive patients presenting to the investigator's clinic, whether in-person or via telehealth methods, who meet inclusion/exclusion criteria should be offered enrollment. As a pragmatic study, potential participants will not be excluded based upon measures of clinical severity or based upon preconceived notions of their likelihood to respond to the study interventions. Chronic migraine patients with medication overuse will be identified just as they are in daily clinical practice – according to the patient's report of headache frequency, headache symptoms, acute medications used and their frequency of use. Patients with excessive use of opioids and butalbital containing medications such that immediate discontinuation, in the opinion of the investigator, will pose an unacceptable risk of withdrawal syndrome and a serious risk to patient safety will be excluded (this is expected to be a very small proportion of patients who have chronic migraine with medication overuse). We anticipate that about 90% of patients who are screened for this study will be eligible and 40% of eligible patients will agree to participate in this study. Thus, in order to meet enrollment targets we estimate that headache specialty centers will have to screen approximately 5-6 patients per month, while general neurology and primary care clinics will have to screen about 2 patients per month. In total, each headache specialty clinic is expected to enroll 24 patients per year, while general neurology and primary care clinics are expected to enroll 8 patients per year.

Recruitment Plan

	# patients screened each month	# patients enrolled each year			
Headache Specialty Clinic	6	24			
General Neurology Clinic	2	8			
Primary Care Clinic	2	8			

Study Visits

Each subject **must** have a research visit at baseline/randomization and at 12 weeks post-randomization. These research visits can occur in-person or using IRB-approved telehealth methods, such as, but not limited to telephone, video, e-mail, and regular mail. Other follow-up visits will occur according to the clinician's usual follow-up patterns (these are clinical visits, not study specified visits).

Baseline/Randomization Visit

a. Case Report Forms: The following case report forms and questionnaires are to be completed at the baseline visit:

- Inclusion/Exclusion Criteria

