- Subject Contact Information
- Subject Demographics
- Headache Characteristics

- Medication Use
- Headache Impact Test 6 (HIT-6)
- PROMIS Pain Interference questionnaire
- Generalized Anxiety Disorder 7 (GAD-7)
- Patient Health Questionnaire 9 (PHQ-9)
- EuroQol 5D (EQ-5D-3L)
- Change in Migraine Therapy
- Migraine Functional Impact Questionnaire (MFIQ)

b. Randomization: Participants are to be randomized within the Medidata Rave online system. (see Appendix for instructions on how to use Medidata Rave) Randomization will be 1:1 to one of the two treatment strategies using a simple randomization technique. Randomization is to occur at the time when migraine prophylactic therapy is to be initiated or optimized. For example, if a patient is to receive a new prophylactic migraine medication, randomization would occur on the same day that the prescription is provided and the patient will start the medication. If it is known that there will be a delay between providing the patient with a preventive prescription and that patient receiving/starting the preventive medication, then randomization should occur at the time the patient will start the preventive. If a patient is going to be started on onabotulinumtoxinA, randomization is to occur on the day of the injections.

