- Clinicians will be instructed to discuss the following with the patient: 1) prophylactic medication is being initiated or current prophylactic medication(s) is/are being adjusted; and 2) as a result, it is expected that migraine frequency will reduce and thus abortive medications will be required less frequently.

g. Headache Diary: Patients will maintain a daily headache diary during the following post-randomization weeks:

- 1-12 (days 1-84)
- 21-24 (days 141-168)
- 45-48 (days 309-336)

At the baseline visit, patients will need to receive instructions on the use of the electronic/internet based headache diary that is within the Medidata Rave system. Patients may choose to use either the online or app version of the diary (or a combination of both). Sign-in information needs to be obtained. A paper headache diary is also to be given to patients along with instructions for use.

This migraine and medication diary will require participants to record whether or not they had a headache on a given day, the maximum severity of headache pain during that day, whether the headache caused no, mild, moderate or severe functional impairment, whether or not they took migraine abortive medications that day (and which medication), whether or not they took migraine prophylactic medication that day, and any changes to their treatment regimen.

Twelve Week Follow-Up Visit

All subjects are to be seen for follow-up at 12 weeks post-randomization (+/- 1 week). This 12-week visit can be accomplished in-person (i.e. in the office) or using IRB-approved telehealth methods, such as, but not limited to telephone, video, e-mail, regular mail, and by completing internet-based questionnaires.

Subjects are to remain in the treatment group to which they were randomized through this 12-week visit. Subjects will remain in this study through week 48, but treatment recommendations starting with week 13 will be according to the clinician's usual clinical practice.

h. Case Report Forms: The following case report forms and questionnaires are to be completed at the 12-week visit:

- Follow-up Visit Headache Characteristics
- Medication Use
- Headache Impact Test 6 (HIT-6)
- PROMIS Pain Interference questionnaire
- Generalized Anxiety Disorder 7 (GAD-7)
- Patient Health Questionnaire 9 (PHQ-9)
- EuroQol 5D (EQ-5D-3L)
- Change in Migraine Therapy
- Migraine Functional Impact Questionnaire (MFIQ)

Other Follow-Up Visits and Telephone Contacts

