 - o Day 146-148 after the baseline visit
 - o Day 153-155 after the baseline visit
 - o Day 160-162 after the baseline visit
- 45-48 weeks post randomization:
 - o Day 307-309 after the baseline visit
 - o Day 314-326 after the baseline visit
 - o Day 321-333 after the baseline visit
 - o Day 328-340 after the baseline visit

k. Changes in Therapy: Changes in the subject's migraine treatment that might occur outside of the follow-up visits (e.g. via a telephone call with the patient) should be documented in the "Medications and Treatments" case report form within Medidata Rave. **10. Study Outcomes**

- **a. Primary Outcome**: The primary outcome measure for this study will be frequency of moderate to severe headache days (i.e. days on which a headache lasts for at least 2 hours and at any time peaks at moderate or severe intensity) per 4 weeks measured during 9-12 weeks postrandomization. If non-inferiority is demonstrated for the primary outcome, then a test of superiority will be performed for the frequency of moderate to severe headache days during the first 2 weeks post-randomization.
- b. Secondary Outcomes frequency of headaches associated with moderate to severe functional impairment, frequency of days taking abortive medications, headache frequency, treatment adherence rates, and rates of subject dropout. (RQ-2) (RQ-6) (PC-3) In addition, relapse rates (i.e. the proportion of subjects who stopped overusing the abortive medication but then returned to the overuse pattern) will be measured using the 21-24 week and 45-48 week data.
 - Frequency of headaches associated with moderate to severe functional impairment
 - Frequency of days taking symptomatic medications
 - Headache Frequency
 - Treatment Adherence Rates
 - Subject Study Dropout Rates
 - Relapse Rates (i.e. the proportion of subjects who stopped overusing the abortive medication but then returned to the overuse pattern)
 - Quality of Life
 - Disability

c. Heterogeneity of Treatment Effects Analyses

- Class of overused medication
- Baseline frequency of taking the overused medication
- Duration of medication overuse

- Years with migraine
- Years with chronic migraine
- Type of provider managing the patient (i.e. headache specialist, general neurologist, primary care physician)
- Frequency of follow-up visits
- Class of prophylactic therapy(s) used
- Baseline headache frequency
- Baseline anxiety and depression scores
- Patient age
- Patient sex
- Type of visit (in person vs. virtual)

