- Calendar period (before or after initiation of virtual visits)

11. Sample Size and Data Analyses Plans

a. Sample Size

The sample size was calculated based upon showing non-inferiority of prophylactic therapy alone compared to prophylactic therapy with early discontinuation of overused medication. An effective sample of 288 per group (80% of 360) has 80% power (two-sided α .05) to determine that the mean difference is less than 1.5 moderate to severe headache days per four weeks, assuming a population difference of 0.0 moderate to severe headache days per four weeks (pooled SD 6.4 from Silberstein 2013).

b. Data Analyses Plans

Patients will be included in the primary analysis on the basis of intention-to-treat. The frequency of moderate to severe headache days during the 9-12 week post-randomization period will be compared among the two treatment groups by using a two-sample t test. The primary test will be a test of noninferiority. The noninferiority margin will be defined as a mean difference of 1.5 moderate to severe headache day per four weeks. A second primary measure will be assessed by using a fixed sequence gatekeeper strategy. If noninferiority is demonstrated for the frequency of moderate to severe headache days during the 9-12 week period, then a test of superiority will be performed for the frequency of moderate to severe headache days during the first 2 weeks postrandomization. Missing values will be handled by multiple imputation. Pattern mixture modeling will be used if the pattern of missing data differs between groups. In addition, baseline characteristics for subjects with missing primary outcome data will be compared to those without missing data. An interim analysis will be performed using data from 12 weeks after the 360th subject has been randomized. Interim analyses will be performed by using the alpha spending function method with a Haybittle-Peto boundary function. Results will be considered statistically significant if the nominal significance level is less than 0.001 at the interim analyses, or less than 0.049 at the final analysis. Per-protocol analyses will be performed in addition to the intention-to-treat analyses because the primary hypothesis is based on noninferiority. The intention-to-treat and per-protocol analyses would both have to demonstrate non-inferiority to consider the trial positive.

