A confirmatory heterogeneity of treatment effect analysis for type of overused medication will be performed if the primary analysis demonstrates noninferiority. (HT-3) Patients will be classified into whether or not the overused medication was an opioid or barbiturate vs. another abortive medication. The frequency of moderate to severe headache days during the 9-12 week period will be compared among the two treatment groups by using a general linear model with terms for group, overused medication category (opioid or barbiturate versus other), and group by category interaction. Descriptive heterogeneity of treatment effect analyses will be performed for duration of overuse, baseline headache frequency, number of years with migraine, number of years with chronic migraine, the type of provider managing the patient (e.g. headache specialist vs. neurologist vs. primary care provider), patient sex, patient age, baseline anxiety and depression scores, the class of prophylactic therapy used, the frequency of follow-up visits with the clinician, type of visit, and calendar period. Analyses concerning prophylactic medications will focus on the therapy that was the change in treatment at the baseline visit. For example, if a participant is

taking medication A at baseline and the clinician adds medication B, it is medication B that would be considered the treatment of interest.

12. Potential Risks and Protection of Human Subjects

The study will be conducted according to Good Clinical Practice guidelines, the Declaration of Helsinki, U.S. 21 Code of Federal Regulations for Protection of Human Subjects, and Institutional Review Boards, and pursuant to state and federal HIPAA regulations. Institutional Review Boards for each participating center must provide unconditional approval prior to that centers participation in this study. Documents proving IRB-approvals will be submitted to the Principal Investigators prior to each center's participation. All protocol amendments will require IRB approvals and documents confirming approval of such amendments will be submitted to the Principal Investigators. Each participating center's IRB and the IRB at the principal investigators' center (Mayo Clinic) will be informed of all serious or unexpected adverse events that occur during the study. Adverse events will also be reported to PCORI, if such reporting of adverse events is consistent with PCORI policy.

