- B. Occurring in a patient who has had ≥5 attacks of migraine with or without aura
- C. On ≥8 days/month for >3 months, fulfilling any of the following:
 - a) migraine without aura diagnostic criteria
 - b) migraine with aura diagnostic criteria
 - c) believed by the patient to be migraine at onset and relieved by a triptan or ergot derivative
- D. Not better accounted for by another headache diagnosis

Medication Overuse Diagnostic Criteria

- A. Regular intake of ergotamine, triptans, opioids, combination analgesics, or a combination of drugs from different classes on ≥10 days per month for >3 months
- B. Regular intake of simple analgesics (e.g. acetaminophen, NSAIDs) on \geq 15 days per month for >3 months

Determining the Optimal Treatment Strategy for Patients who have Chronic Migraine with Medication Overuse

Contact Information

Name:(First)		(Last)	
Home: ()		Work: ()	-
Mobile: ()		Email:	
Address:			
		Unit/Apt#	
(Street)			
City	State	Zip	

Determining the Optimal Treatment Strategy for Patients who have Chronic Migraine with Medication Overuse

Subject Demographics

DOB:/	
Current age (years):	
Sex at birth (circle one): 1 = Male	2 = Female
Race (circle all that apply):	
1 = American Indian/Alaska Native	2 = Asian
3 = Black/African American	4 = Native Hawaiian/Other Pacific Islander
5 = White/Caucasian	6 = Other

Ethnicity: 1 = Hispanic 2 = Non-Hispanic

Determining the Optimal Treatment Strategy for Patients who have Chronic Migraine with Medication Overuse

Headache Characteristics

On average over the last 3 months, how many days per month (30 days) with headache of any kind/severity : days
On average over the last 3 months, how many days per month (30 days) with complete headache freedom : days
How many days over the last 30 days with headache that at any time during the day became moderate or severe intensity: days
On those days when headache intensity became moderate or severe, on average how many hours did the pain remain moderate or severe ? hours
How many days in the last 30 days did the headache remain mild intensity all day long? days
How many days in the last 30 days have acute (as needed) medications (e.g. triptans, analgesic) been taken for headache?
How many days in the last 30 days have analgesic (pain) medications been taken for conditions other than headache (e.g. other pain, fever)? days
How many days in the last 30 days have no analgesic or acute medications been taken? days

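### The primary noninferiority t test is valid, but it ignores a baseline count of moderate-or-severe headache days that the trial already collects, and so gives up precision

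*Combined protocol and SAP*

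**What the plan says.** Section 11b, Data Analyses Plans, states that the weeks 9-12 frequency "will be compared among the two treatment groups by using a two-sample t test", as a noninferiority test against a margin of 1.5 days per four weeks. Both the intention-to-treat and the per-protocol analysis must pass. The nominal level is 0.001 at the interim look and 0.049 at the end. No covariate is named.

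Section 11a sizes the trial at 288 effective participants per group, "assuming a population difference of 0.0 moderate to severe headache days per four weeks (pooled SD 6.4" from a cited study). It does not say whether that SD belongs to the count or to change from baseline.

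A related baseline value is collected. Section 9, item a of the baseline visit, says "The following case report forms and questionnaires are to be completed at the baseline visit", and the list includes Headache Characteristics. That form, in appendix 21a, asks "How many days over the last 30 days with headache that at any time during the day became moderate or severe intensity".

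The outcome in section 10a is narrower: "days on which a headache lasts for at least 2 hours and at any time peaks at moderate or severe intensity". It comes from a diary that starts only after randomisation (section 9g: "Patients will maintain a daily headache diary during the following post-randomization weeks").

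Section 9b says "Randomization will be 1:1 to one of the two treatment strategies using a simple randomization technique", so the design does not balance baseline frequency. In the analysis plan, baseline headache frequency appears only as a descriptive heterogeneity factor. The one linear model planned for this outcome, the confirmatory heterogeneity analysis, works "by using a general linear model with terms for group, overused medication category (opioid or barbiturate versus other), and group by category interaction", also without the baseline count.

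**The concern.** Noninferiority here turns on whether the upper confidence limit for the difference (without minus with immediate discontinuation) stays below 1.5 days, so the width of the interval decides the result. An unadjusted comparison leaves in the standard error all the outcome variation that baseline frequency could have explained. Part of that variation is chance imbalance between arms at baseline, which simple randomisation does not limit.

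The plan has little slack. It reaches 80% power only if the true difference is exactly zero, and two analysis sets must both succeed. A strategy that is truly noninferior could miss the margin because available information was not used.

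**Working it through.** **Inputs.** Margin 1.5, true difference 0, SD 6.4, 288 per group and two-sided alpha 0.05 (section 11a); final nominal alpha 0.049, one-sided 0.0245 (section 11b). The baseline-outcome correlation r is not given, so a range is assumed.

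**Reproducing the plan.** SE = 6.4 × √(2/288) = 0.533. The normal-approximation sample size is 286 per group at one-sided 0.025 and 288 at 0.0245; 288/0.80 = 360 randomised per group. Noncentral t power (574 df) is 80.2% at 0.025 and 79.9% at 0.0245. The stated sample size is right for the stated test.

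**Reading 1: 6.4 is the SD of the weeks 9-12 count.** The ANCOVA residual SD is 6.4 × √(1 − r²), with 573 df. The half-width is the t critical value (1.973) × SE, and the largest observed difference that still passes is 1.5 minus the half-width.

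| r | Residual SD | Power | CI half-width (days) | Largest passing difference (days) |
|---|---|---|---|---|
| t test | 6.40 | 79.9% | 1.05 | 0.45 |
| 0.1 | 6.37 | 80.3% | 1.05 | 0.45 |
| 0.2 | 6.27 | 81.5% | 1.03 | 0.47 |
| 0.3 | 6.11 | 83.5% | 1.00 | 0.50 |
| 0.4 | 5.87 | 86.3% | 0.96 | 0.54 |
| 0.5 | 5.54 | 89.9% | 0.91 | 0.59 |
| 0.6 | 5.12 | 93.8% | 0.84 | 0.66 |

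**Reading 2: 6.4 is the SD of change.** With equal variances at the two times, the count SD is 6.4/√(2(1 − r)), and the residual SD is that times √(1 − r²).

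| r | Count SD | t test power | ANCOVA power |
|---|---|---|---|
| 0.1 | 4.77 | 96.4% | 96.5% |
| 0.3 | 5.41 | 91.2% | 93.5% |
| 0.5 | 6.40 | 79.9% | 89.9% |
| 0.7 | 8.26 | 58.2% | 85.9% |

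**Chance imbalance.** Under reading 1, a baseline difference of 1.96 standard errors moves the unadjusted estimate by r × 1.96 × 6.4 × √(2/288) = r × 1.045 day. That is 0.10, 0.31 or 0.52 day at r = 0.1, 0.3 or 0.5; the baseline SD cancels. This is the same precision loss viewed conditionally, not a further one.

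**Cost if r = 0.** Variance rises by a factor of about 1 + 1/(576 − 4) = 1.0017.

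**Bounded counts.** A simulation (20,000 runs per case) used integer outcomes from 0 to 28 with SD 6.4 and an assumed mean of 12, and integer baselines truncated to 8-30. Power for the t test versus ANCOVA was 79.8% vs 80.1% (realised r = 0.10), 80.0% vs 83.4% (0.30) and 80.0% vs 89.7% (0.49). The one-sided type I error of ANCOVA at a true difference of 1.5 was 0.0242 to 0.0253 against nominal 0.0245 (Monte Carlo SE 0.0011).

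**The case against.** The strongest reply is that nothing is broken. The t test is valid, the sample size meets its own 80% target, and the documents contain no figure for the gain. Several features could hold r down: recall rather than diary, no 2-hour rule, an entry criterion of at least 15 headache days and 8 migraine days per month that restricts the baseline range, and a change of prophylaxis for every participant at randomisation. At r = 0.1 the gain is 0.4 points. All of this stands. It limits the size of the claim, but does not favour leaving the covariate out, because the loss at r = 0 is negligible.

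The change is also more than code. The analysis plan is part of the protocol, so it needs an amendment with IRB approval (section 12) and a logged new version sent to sites (section 17). That is true, but it is routine paperwork.

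Some baseline counts may be missing, since section 15 lets data be entered when required fields are not satisfied. That also stands, and calls for a stated rule. Reading 2 rests on an ambiguity in section 11a rather than on evidence that 6.4 is a change SD; it is shown as a range only. Multiple imputation might already include baseline, but the plan does not say so, and imputation would not recover precision among participants with observed outcomes.

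**Conclusion.** The concern holds as an avoidable loss of efficiency, worth correcting but not a flaw in validity. Under either reading of the SD, adjustment adds less than 2 percentage points of power at r of 0.2 or less and about 10 points at r = 0.5. Under reading 1 it adds 3.6 points at r = 0.3 (83.5 − 79.9). Which r applies cannot be settled from the documents, and the gain may be modest. The conclusion does not depend on r being large: the covariate is measured before randomisation, so its imperfections can weaken the gain without biasing the comparison, and in expectation ANCOVA loses essentially no precision at this sample size. The figures assume a true difference of zero, 288 evaluable per group and a linear baseline relation with the same slope in both arms.

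**What to change.** - Make the primary analysis an ANCOVA of weeks 9-12 moderate to severe headache days on arm and the baseline 30-day count of moderate-or-severe headache days. Declare noninferiority if the upper limit of the adjusted two-sided 95.1% interval is below 1.5.
- Use the same model in the intention-to-treat and per-protocol sets and at the interim look (at its 0.001 level). Make the same adjustment in the superiority test for the first 2 weeks.
- Put the baseline count in the imputation model, and state that missing baseline counts will be imputed.
- Keep the two-sample t test as a sensitivity analysis.
- State in section 11a whether SD 6.4 is for the count or for change.
- Provider type could be an additional covariate, but it is optional. It would have to be derived from the site, because no baseline form shown records it.

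The cost is a protocol amendment, model code and one degree of freedom. No new data are needed, and the 30-day scale needs no conversion because the count enters as a covariate. The margin, alpha, sample size and target difference in means do not change. The amendment must be fixed before anyone sees unblinded data.
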